8.5.3 Analysis of secondary efficacy endpoint(s)

The analysis of selected secondary efficacy endpoints will be performed on the FAS, mFAS, Non-restricted FAS and PP populations. The remaining secondary endpoints will be analysed on the FAS Population only.

8.5.3.1 Tr. vBMD (tibia) on HRpQCT

Descriptive summary tables will be presented for HRpQCT results for the Tr. vBMD (tibia) ,change from baseline and percentage change from baseline in Tr.vBMD (tibia) on HRpQCT results by treatment group and visit.

The log transformed change from baseline in Tr.vBMD (tibia) on HRpQCT will be analysed via ANCOVA in the same manner as the change from baseline in Tr.vBMD (radius) on HRpQCT (see Section 8.5.2.1). This analysis will be conducted on the FAS, Non-restricted FAS, mFAS and PP populations.

8.5.3.2 DXA BMD

Descriptive summary tables will be presented for DXA Lumbar, Whole Body and Proximal femur BMD values and percentage change from baseline values by treatment group and visit.

The percentage change from baseline in for DXA Lumbar, Whole Body and Proximal femur BMD will also be analysed via ANCOVA in the same manner as the change from baseline in Tr.vBMD (radius) on HRpQCT (see Section 8.5.2.1). This analysis will be conducted on the FAS, Non-restricted FAS and PP populations. A similar analysis will be conducted on the associated DXA Lumbar, Whole Body and Proximal femur BMD change from baseline T-scores.

8.5.3.3 Vertebral Assessments

All vertebral endpoints will be analysed on the FAS Population and PP Population only.

8.5.3.3.1 Vertebral Fractures

For all vertebral assessments the X-ray scans will be used as source.

The number and proportion of patients with a new vertebral fracture and new or worsening vertebral fracture will be summarised by treatment group throughout the treatment period (at each visit). In addition, a P-value for the comparison between each group will be provided using a Chi squared test.

The total number of new vertebral fractures and new or worsening vertebral fractures per patient during the treatment period will be compared between each treatment group using a poisson regression model as described in section 8.5.1. An estimate of the ratio of new vertebral fractures and new or worsening vertebral fractures between treatment groups will be presented together with a two-sided 95% confidence interval and P-value.

For patients that have a vertebral fracture a shift table of the change in fracture grade will be presented. The number and percentage of patients with each level of change (from worst baseline grade to worst post-baseline grade) will be displayed.

Finally the total sum of vertebral fracture grades will also be analysed via ANCOVA in the same manner as the change from baseline in Tr.vBMD (radius) on HRpQCT (see Section 8.5.2.1).

8.5.3.3.2 Vertebral Height

Vertebral height derived from 6-point quantitative morphometry will be summarized at 6 and 12 months. The mean (across all vertebrae) Anterior, Mid and Posterior heights, HA/HP ratio and HM/HP ratio will be summarised descriptively.

The maximum change from baseline in the HA/HP and the HM/HP ratio for fractured vertebrae will be analysed using ANCOVA in the same manner as the change from baseline in Tr.vBMD (radius) on HRpQCT (see Section 8.5.2.1).

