Secondary	
 • Tr. vBMD (tibia): An ANCOVA will be calculated on log transformed data as described above on the FAS, mFAS, the PP population, the FAS and the Non-Restricted FAS in both versions • DXA BMD: Changes will be compared treatment groups using an ANCOVA as described above on the percent change from baseline and on the T-scores for the following variables on the FAS, the PP population, the FAS and the Non-Restricted FAS in both versions: 
 ○ Lumbar BMD ○ Whole body BMD ○ Proximal femur BMD • Vertebral assessments: 
 ○ Vertebral fractures assessed by Genant's semi-quantitative method: 
 ▪ 2x2 table analysis for occurrence of new and new or worsening fractures (yes/no) ▪ Poisson regression for number of new and new or worsening fractures, if appropriate

Endpoint	Statistical Analysis Methods
	
 ▪ Shift tables to investigate the change in grade for existing fractures ▪ An ANCOVA with baseline value as covariate and treatment group and stratum as factors to investigate the percent change from baseline in numbers of vertebral fractures ▪ An ANCOVA with baseline value as covariate and treatment group and stratum as factors to investigate the total sum of vertebral gradings 
 ○ Vertebral height derived from 6-point quantitative morphometry: The maximum change from baseline in the H_A/H_P and the H_M/H_P ratio for fractured vertebrae will be analysed using ANCOVA • Change in bone histomorphometry • HRpQCT parameters: 
 ○ Total vBMD ○ Cortical vBMD ○ BV/TV ○ Met/Inn ○ TbTh ○ TbN ○ Inhomogeneity ○ Cortical thickness ○ Cortical porosity (tibia and radius) • Body composition: Comparisons between treatment groups will be performed using an ANCOVA as described above 
 ○ Body height ○ Body weight ○ BMI ○ Lean body mass ○ Fat body mass • Change from baseline to each visit for bone turnover markers and metabolic biomarkers • Fracture rate: Chi square tests will be calculated to assess differences across treatment groups on the following on the FAS, the PP population, the FAS and the Non-Restricted FAS in both versions: 
 ○ Total fracture rate ○ Peripheral fracture rate

Endpoint	Statistical Analysis Methods

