8.1.4 Statistical significance

Unless otherwise stated, all statistical testing will be two-sided and conducted at the significance (alpha) level of 0.05. Two-sided 95% confidence intervals (CIs) will be provided when relevant.

For the primary analysis the LSMeans for each blinded treatment group will be calculated and tested against the null hypothesis of 0 in an a priori hierarchical approach, starting with the highest dose.

For secondary and exploratory endpoints treatment groups will be assessed by pairwise comparisons for secondary efficacy data, and no adjustment for multiplicity will be made.

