8.5.1 Analysis methods

For all continuous outcomes, where appropriate, an ANCOVA model analysis will be performed. Analyses will include the fixed, categorical effects of treatment and randomisation stratum as well as the associated baseline value as a covariate. Significance tests for treatment differences (between Setrusumab doses) will be based on least-squares means (LSMeans).

ANCOVA analyses dealing with nested observations within a patient (e.g., vertebral assessments) will consider this relationship in the modelling by specifying patient as a random factor.

If the input data is log-transformed then LSMean and LSMeans differences between treatment groups will be back-transformed to their original scale for descriptive purposes. After subtracting the geometric mean of the log baseline values, the back-transformed LSMeans will correspond to the percentage change from baseline, while the back-transformed LSMeans differences will correspond to the ratio of percentage changes from baseline.

Time to event variables (e.g., time to first fracture) will be analysed using Kaplan-Meier methods, and quartiles for the median time to event will be presented together with their 95% confidence intervals.

Count variables (e.g number of new fractures) will be analysed using Poisson regression. Analyses will include treatment and randomisation as fixed effects and the logarithm of the duration of exposure to study medication will be included as an offset variable in the model. In case over dispersion is a concern, the negative-binomial regression model will be applied instead.

For binary outcomes the proportion of patients with a response will be summarised and compared between treatment groups using Chi squared test.

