8.5.2.1 Primary analysis

The HRpQCT results for the Trabecular vBMD (radius) will be log transformed and an ANCOVA model will be used to calculate the LSMMeans for the change from baseline as described in Section 8.5.1. The change from baseline LSMMeans for each treatment group will be tested against the null hypothesis of 0 using a t-test, in an a priori hierarchical approach, starting with the highest dose.

The LSMMeans and standard errors will be displayed at each visit as well as the corresponding P-value from each t-test.

Differences between LSMMeans, their confidence intervals and P-values will also be displayed but will be analysed in an exploratory fashion only. The type I error rate will be 5% two-sided. P-values above 5% but below 10% (two-sided) will be considered as indicative for a trend.

LSMeans and LSMeans differences between treatment groups will be back-transformed to their original scale for descriptive purposes. After subtracting the geometric mean of the log baseline values, the back transformed LSMMeans will correspond to the percentage change from baseline, while the back-transformed LSMMeans differences will correspond to the ratio of percentage changes from baseline.

Line graphs of the LSmean HRpQCT results (+/- SE) and change from baseline in HRpQCT results (+/- SE) will be presented.

A descriptive summary will also be presented for the non-log transformed HRpQCT results for the Trabecular vBMD (radius) values, change from baseline and percentage change from baseline in HRpQCT by treatment group and OI type.

For supportive evidence, the above analysis will be repeated on the mFAS, Non-restricted FAS in both versions and the PP population for HRpQCT results for the Trabecular vBMD (radius) and repeated for the bone strength on FEA for the FAS, Non-restricted FAS and PP population.

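### Vertebral height: the maximum ratio change is left undefined, and testing it against 0 within each arm can give false significance from noise alone

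*SAP*

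**What the plan says.** SAP 8.5.3.3.2 defines the tested variable: "The maximum change from baseline in the HA/HP and the HM/HP ratio for fractured vertebrae will be analysed using ANCOVA". Protocol 11.3.1 has the same rule: "The maximum change from baseline in the H_A/H_P and the H_M/H_P ratio for fractured vertebrae will be analysed using ANCOVA". Neither document says:

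- whether the maximum is taken per participant or per vertebra;
- whether it is taken over vertebrae or over visits;
- whether it is signed or absolute, or a gain or a loss;
- whether a vertebra counts as fractured at baseline, at follow-up or at either time.

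The SAP sentence then says the analysis follows the method for radial Tr. vBMD in 8.5.2.1, where the LSMean change "for each treatment group will be tested against the null hypothesis of 0 using a t-test". SAP 8.5.3.3 restricts vertebral endpoints to the FAS and PP sets, which contain only the three blinded active arms.

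Two other rules bear on this analysis. SAP 8.1.4 says that "treatment groups will be assessed by pairwise comparisons for secondary efficacy data, and no adjustment for multiplicity will be made". SAP 8.5.1 says that "ANCOVA analyses dealing with nested observations within a patient (e.g., vertebral assessments) will consider this relationship in the modelling", with patient as a random factor.

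**The concern.** A test against 0 is valid only if the variable has mean 0 when nothing has changed. A single vertebra's measured change at a fixed visit meets that condition. The largest of several noisy changes does not: its mean lies above 0 and rises with the number of changes compared. The largest loss has the same bias downwards. The analysis sets contain no control arm in which the same bias would appear and cancel.

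At stake is a within-arm significance statement on a named secondary objective, vertebral height. Depending on the reading, it could show apparent improvement or apparent deterioration in every arm. There is a second risk for the dose comparisons. If vertebrae that fracture on treatment count as fractured, the number of vertebrae behind each maximum can differ by dose, and a difference in fracture counts would then look like a difference in height change.

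**Working it through.** **The plan's own figure.** There is none to reproduce. The documents give no power, error rate, measurement error or number of fractured vertebrae for this endpoint.

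**Inputs from the documents.** Two-sided alpha is 0.05 (SAP 8.1.4). There are three blinded arms with 25 planned per arm (SAP 5), which is an upper limit here because only participants with a fractured vertebra contribute. The ANCOVA has treatment, stratum and baseline (SAP 8.5.1). The visits are Months 6 and 12.

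**Assumptions.** True change is 0; errors are normal and independent; there are k = 1 to 5 fractured vertebrae per participant and n = 10 to 25 contributing participants per arm.

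**Step 1: bias of the maximum, in SDs of a single change.** Expected values are 0 (k = 1), 0.57 (k = 2), 0.85 (k = 3) and 1.16 (k = 5). For k = 2 the exact mean is √(1/π) = 0.564 and the SD is √(1 − 1/π) = 0.826.

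**Step 2: hand check of the test against 0, k = 2.** The standardised shift is √n × 0.564/0.826. Residual df = 3n − 5.

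- n = 25: shift 3.42, critical value 1.99 (70 df), rejection ≈ Φ(1.43) = 92%.
- n = 10: shift 2.16, critical value 2.06 (25 df), rejection ≈ Φ(0.10) = 54%.

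**Step 3: simulated ANCOVA** (log ratio, 1,500 runs per setting, simulation error at most about 1.3 points), rejection of no change within an arm:

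| Variable | n = 10 | n = 25 |
|---|---|---|
| Largest signed change, k = 1, one visit | 6% | 5% |
| Largest signed change, k = 2 | 55% | 94% |
| Largest signed change, k = 3 | 95% | 99.9% |
| Largest signed change, k varying 1 to 4 | 54% | 91% |
| Largest decrease, k = 2 | 52% | 91% |
| Largest over two visits, k = 1 | 28% | 59% |
| Absolute change, k = 1 | 99% | 100% |
| Signed change of largest magnitude, k = 1 to 5 | 5–6% | 5–6% |
| Mean change over vertebrae, k = 1 to 5 | 4–6% | 5–6% |

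Measurement SD hardly matters: at n = 15, k = 3 the rate is 99% with SD 0.01 and with SD 0.05. A plain one-sample t-test gives 91% at n = 25, k = 2. For sparser data it gives 16% (n = 12, k of 1 or 2) and 31% (n = 10, k of 1 to 3).

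**Step 4: correlation between vertebrae.** With correlation ρ and k = 2, the mean is √((1 − ρ)/π) and the variance is 1 − (1 − ρ)/π. At an assumed ρ = 0.5 these give mean 0.399 and SD 0.917.

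- n = 25: shift 5 × 0.399/0.917 = 2.18, so Φ(2.18 − 1.99) ≈ 57%.
- n = 10: shift 3.16 × 0.399/0.917 = 1.38, so Φ(1.38 − 2.06) ≈ 25%.

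The inflation is smaller but remains.

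**Step 5: differences between doses.** With equal counts and equal noise, the 20 versus 2 mg/kg comparison rejects in 3.5% to 6.9% under every rule. With unequal counts it does not hold its level: 1 versus 2 vertebrae gives 26% (n = 10) to 57% (n = 25), and 2 versus 3 gives 12% to 24%.

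**Step 6: selection of fractured vertebrae.** As an illustration, take true ratios with mean 0.90 and SD 0.07, measurement SD 0.03, and call a ratio below 0.80 fractured. Noise alone then gives a mean change of +0.020 if selected at baseline, −0.021 if selected at follow-up, −0.053 for new fractures only, and about 0 if selected at either time.

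**The case against.** The strongest reply is that the calculation rests on one reading. The text does not say the maximum is per participant, and there is no inflation with one fractured vertebra at one visit or with the signed change of largest magnitude. That stands, and it makes the result conditional.

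The 91–94% figures need all 25 participants in an arm to have two fractured vertebrae. The protocol's inclusion criteria admit people on non-vertebral fractures alone, so smaller and mixed cases are more plausible. Vertebrae in one participant share images, and positive correlation reduces the bias. Both points stand and are reflected in the range.

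The random-factor rule in SAP 8.5.1 arguably already reaches this analysis, because 8.5.2.1 refers back to 8.5.1. So a reader should not conclude that the SAP ignores nesting. The difficulty is that a single maximum per participant leaves nothing to nest, so the two rules do not fit together.

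SAP 8.1.4 emphasises pairwise comparisons for secondary endpoints, and these hold about 5% when counts and noise are equal. The protocol mentions only ANCOVA; the test against 0 enters through the SAP's cross-reference. SAP 8.5.3.3.2 also summarises mean ratios across all vertebrae, without a maximum. These points limit the harm, but the test against 0 remains in the plan as written.

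**Conclusion.** The point holds in conditional form. For a signed maximum over two or more fractured vertebrae, or over two visits, the within-arm test against 0 is not valid. Under independent errors its false-positive rate is about 16% to 31% in sparse settings (10 to 12 participants, 1 to 3 vertebrae), and 55% to 91–94% with two vertebrae each (10 to 25 participants). These rest on assumed counts, and correlation would lower them. Since the rate runs from 5% to 100% across readings the text allows, the analysis is not adequately pre-specified.

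A reader might infer three stronger things that the documents do not support:

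- **That noise will certainly produce significance.** Some permitted readings give about 5%.
- **That the analysed set depends on outcome.** This follows only if post-baseline fractures count. SAP 7.1.3.2 defines new fractures separately, and 8.5.3.3.2 leaves the matter open.
- **That dose comparisons are invalid.** They are distorted only if fractured-vertebra counts or noise differ between arms.

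This is an unadjusted secondary analysis. It should be corrected, but it does not touch the primary conclusion.

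**What to change.** In SAP 8.5.3.3.2, replace the maximum by vertebra-level change in HA/HP and HM/HP at a named visit, for all vertebrae readable at baseline and at that visit. Fit a mixed model with treatment, stratum, the vertebra's own baseline ratio and patient as a random effect, as SAP 8.5.1 already provides. Repeat it on vertebrae fractured at baseline only, as a supportive analysis.

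State that inference rests on differences between doses, and drop the within-arm test against 0 for this variable. Changing the model alone is not enough: regression to the mean still biases that test for vertebrae selected as fractured at baseline (Step 6).

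The cost is SAP wording, a note in SAP section 9 recording the departure from protocol 11.3.1, and one model. The data are already planned for collection. The downside is that a worst-vertebra summary is no longer the tested variable; it can still be shown descriptively once its direction, visit and vertebra set are defined.

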8.5.3.4 Bone Histomorphometry

Changes in bone histomorphometry parameters will be analysed using ANCOVA in the same manner as the change from baseline in Tr.vBMD (radius) on HRpQCT (see Section 8.5.2.1) using the FAS population only.

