Bone Biomarkers		X	X		X			X				X			X	Fasting pre-dose blood draw, Sub-set of patients will have additional blood draws at 8 d post- baseline (+4 days) and 14 d post-M9 visit.
Bone Biopsy								X							X	Sub-set of participants. Completed once either at M6 or M12
Audiometry	X														X	This procedure can be omitted if the investigative site does not have the capability to complete the audiometry assessment
Patient-Reported Outcomes		X	X		X			X			X				X	

Procedure	Screening (up to 28 days before Day 1)	Months													Notes All visits ± 4 days.	
		Base-line	1	2	3	4	5	6	7	8	9	10	11	EOT/12		
Setrusumab PK		X	X	X	X			X							X	Sub-set of patients will have additional blood draws at 8 d post-baseline. Samples taken pre-dose and 10 mins post-dose at treatment visits. One sample taken at non-treatment visits
Anti-setrusumab Antibodies		X	X	X	X			X							X	Sub-set of patients will have additional blood draws at 8 d post baseline. Taken pre-dose for treatment visits
Zoledronic acid treatment															X	Optional. Can be administered up to 2 months following the visit
AE/SAE/AESI review		←-----→														
Concomitant medication & physical aid/treatment review		←-----→														

3. Schedule of Activities (SoA) Follow-Up Period

Procedure	Months					Notes All visits \pm 4 days.
	14 (Follow-up visit +60 days)	16	18	21	24	
Follow-up call		X		X		
Brief physical examination	X		X		X	
Urine pregnancy tests (WOCBP)	X					
Safety Laboratory assessments	X		X		X	
25-OH-Vitamin D	X		X		X	
12-lead ECG	X					
Vital signs	X		X		X	
HRpQCT			X		X	Scans be conducted \pm 7 days of visit
DXA			X		X	Calcium tablets should not be taken 2 hours prior to DXA lumbar scan
Vertebral Radiograph			X		X	
Fracture Assessment & Radiograph	←-----→					Radiographs will be taken in the event of a symptomatic fracture
Patient-Reported Outcomes			X		X	
Setrusumab PK	X					One sample taken at non-treatment visits

Procedure	Months					Notes All visits ± 4 days.
	14 (Follow-up visit +60 days)	16	18	21	24	
Anti-setrusumab Antibodies	X					
CTX-1 & P1NP	X		X			Tested locally. ± 2 months of visit
Zoledronic acid treatment			X			Optional. Can be administered ± 1 month from visit
AE/SAE/AESI review	←-----→					Reporting only SAEs only after Month 14
Concomitant medication & physical aid/treatment review	←-----→					

4. Introduction

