4.3. Benefit/Risk Assessment

Since there are no approved pharmacological therapies for OI, patients participating in this study have the possibility to receive a potentially beneficial treatment, at a potentially therapeutic dose for a period of time considered long enough to achieve a benefit. It is expected that at least one of the doses of setrusumab will be sub-therapeutic; therefore patients randomised to this dose are not expected to receive any therapeutic benefit from participation. However, no proven therapy will be withheld during the study until the final analysis is performed when all subjects in the blinded treatment arms have completed 12 months of treatment with setrusumab. Data from this study will provide confirmation about whether setrusumab is efficacious for the treatment in adult osteogenesis imperfecta.

The procedures being undertaken in the study are not expected to present any risk to participants. Radiation doses are kept to a minimum; HRpQCT uses a relatively low dose of radiation which is confined to the periphery and avoids exposure of radiologically sensitive organs. Bone biopsy may be unpleasant for participants, but this will not be mandatory and will be done as an optional sub-study.

In non-clinical and early clinical studies with setrusumab, no safety concerns have been identified and the maximum dose proposed for the current study is well below the NOAEL from non-clinical studies. Further information can be found in the IB.

More detailed information about the known and expected benefits and risks and reasonably expected AEs of setrusumab may be found in the IB and Participant Information Leaflet.

5. Objectives and Endpoints

Objectives	Endpoints
Primary	

 To demonstrate that setrusumab increases radial trabecular volumetric bone mineral density (Tr. vBMD) on high resolution peripheral quantitative computed tomography (HRpQCT) and bone strength on finite element analysis (FEA) in patients with OI Type I, III or IV 	
 Tr. vBMD (radius) on HRpQCT and bone strength on FEA at 12 months.
Secondary	

 To determine the dose-response relationship of Tr. vBMD to setrusumab after 12 months of treatment 	
 Tr. vBMD (radius) on HRpQCT at 12 months.

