10.1.2. Bone Biopsy

Bone biopsies will be performed once at either Month 6 or Month 12 in a sub-set of participants. Informed consent will be obtained using a specific bone biopsy consent form.

Double labelling of bone, according to the procedure detailed in the MBPS205 Bone Biopsy Manual, will be carried out before the bone biopsy procedure to allow determination of the level of bone turnover, and bone formation and mineralisation rates.

All biopsies will be analysed at a central laboratory as per the MBPS205 Bone Biopsy Manual.

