8.1.5 Definition of Baseline

Unless otherwise stated, Baseline will be the last assessment value before first study dose of study medication. For patients that were randomised to placebo prior to protocol amendment 4.0, assessments taken while on placebo may be utilized for the baseline derivation of each parameter.

For HRpQCT scan parameters baseline assessments maybe collected up to 10 days post the first dose of study medication.

Change from Baseline is defined as (value at assessment date – baseline value).

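### Bone histomorphometry is assigned a change-from-baseline ANCOVA, but no pre-dose biopsy is scheduled, so the model has no usable records

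*SAP*

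**What the plan says.** **Analysis.** SAP 8.5.3.4 reads: "Changes in bone histomorphometry parameters will be analysed using ANCOVA in the same manner as the change from baseline in Tr.vBMD (radius) on HRpQCT", and restricts the analysis to the FAS. The model it points to is set out in three places:

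- SAP 8.5.1 fits treatment and randomisation stratum "as well as the associated baseline value as a covariate".
- SAP 8.5.2.1 adds the test: "The change from baseline LSMMeans for each treatment group will be tested against the null hypothesis of 0 using a t-test".
- SAP 8.1.5 defines the reference value: "Baseline will be the last assessment value before first study dose of study medication".

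**Data collection.** Protocol 10.1.2 says "Bone biopsies will be performed once at either Month 6 or Month 12 in a sub-set of participants". The note in the Schedule of Activities (Protocol section 2) agrees: "Completed once either at M6 or M12". The biopsy row is marked at Month 6 and Month 12 only. Protocol 4.3 says of biopsy that "this will not be mandatory and will be done as an optional sub-study". The size of the sub-set is not stated.

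**Endpoint.** Protocol section 5 and SAP 4.2 list the secondary endpoint as changes in bone histomorphometry. Protocol 11.3.1 lists it in similar terms and names no specific model for it.

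**The concern.** The prescribed analysis needs a pre-dose and an on-treatment value from the same participant. The schedule provides only the on-treatment value. Run as written, the ANCOVA would return nothing, and a replacement would have to be chosen once the data were in hand, possibly after unblinding. What is at stake is the only inferential analysis specified for this endpoint, and whether the endpoint can be derived as a within-patient change.

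**Working it through.** The documents give no sample size, power or expected value for histomorphometry, so there is no planned figure to reproduce. The check compares what the model needs with what the schedule supplies.

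**1. What the model needs**

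- Response: change = on-treatment value − baseline value, or the difference of logs if the log transformation of SAP 8.5.2.1 is carried over.
- Covariate: the baseline value.
- Biopsies needed per participant: 1 pre-dose + 1 on-treatment = 2.

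**2. What the schedule supplies**

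- Pre-dose biopsies: 0. The Schedule of Activities has no biopsy mark at Screening or Baseline. The bone-biopsy note on the informed-consent row concerns consent, not a procedure.
- On-treatment biopsies: 1, at Month 6 or Month 12.
- Total: 0 + 1 = 1, one short of the 2 required.

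**3. Complete records**

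A record is complete only if both values exist. With n biopsied FAS participants, complete records = n × 0 = 0. The sub-set size is not stated, so the sizes below are assumptions. The largest is the planned FAS, 3 blinded arms × 25 = 75 (SAP section 5).

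| Biopsied FAS participants (assumed) | On-treatment values | Complete ANCOVA records |
|---|---|---|
| 10 | 10 | 0 |
| 25 | 25 | 0 |
| 50 | 50 | 0 |
| 75 | 75 | 0 |

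The zero follows directly from the schedule; the table only shows that it does not depend on the sub-set size.

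**4. Could another rule supply a baseline?**

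- *Late baseline.* SAP 8.1.5 accepts baseline values up to 10 days after first dose, but for HRpQCT only.
- *Placebo-period values.* SAP 8.1.5 lets these serve as baseline for patients randomised to placebo before amendment 4.0. SAP 6.1 excludes those patients from the FAS, the only set used here.
- *Month 6 as reference for Month 12.* Excluded, because each participant is biopsied once.
- *Imputation.* SAP 7.2.1 uses observed cases without imputation for summary tables, and no separate rule is given for this ANCOVA.
- *Protocol version.* The SAP cites Amendment 5. The change log in Protocol Appendix 9 shows that the text before Amendment 6 had a Month 6 biopsy only, so that version had no baseline biopsy either.

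**5. Could the model be run on the measured value instead?**

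Not as specified. The baseline covariate would still be missing, and a test of a measured value against zero would no longer be a test of change.

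**The case against.** The strongest reply is that the plan already has room to cope. SAP 8.5.1 is qualified: "For all continuous outcomes, where appropriate, an ANCOVA model analysis will be performed". SAP 8.1.3 provides descriptive statistics on observed cases for continuous variables, and SAP section 1 requires deviations to be explained in the study report. The likely outcome is then a descriptive table with a note, and any programmer would see the missing baseline at once. This softens the consequence. It does not remove the mismatch, because 8.5.3.4 commits this endpoint to ANCOVA specifically and names no fallback. By contrast, SAP 8.5.3.5 does write in an exception for Month 3, where only the open-label arm is scanned.

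A second reply is that the endpoint does not say from baseline, unlike many of its neighbours, and could loosely mean drug-related alterations seen at biopsy. Protocol 10.1.2 says double labelling allows turnover, formation and mineralisation rates to be determined, and Protocol 6.4 speaks of a qualitative examination. So a single biopsy can inform the bone-quality objective. That stands as a point about the endpoint, but it does not rescue the ANCOVA.

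Third, comparing measured on-treatment values between doses, with treatment and stratum in the model, can be estimated. That also stands: making the analysis purely descriptive is a preference, and only the change score, the baseline covariate and the test against zero are impossible.

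**Conclusion.** The concern holds. The ANCOVA in SAP 8.5.3.4 has 0 usable FAS records at any sub-set size, because the schedule gives 0 pre-dose biopsies and 1 on-treatment biopsy per biopsied participant. This rests on the published schedule alone; the sub-set sizes tabulated are illustrative. Read as a within-patient change, the endpoint cannot be derived.

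Severity is minor. One secondary endpoint in an optional sub-set is affected. Descriptive summaries of the measured values can still be produced under the general methods of Protocol 11.3 and SAP 8.1.3. No primary, safety or dose-selection result depends on it.

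**What to change.** In SAP 8.5.3.4:

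- Define the variable as the histomorphometry value at the single on-treatment biopsy, and summarise it descriptively by dose group and biopsy month (6 or 12).
- Remove the change-from-baseline ANCOVA, the baseline covariate and the test against zero.
- If a between-dose comparison of measured values is wanted, state its model and label it exploratory, since the sub-set is optional and its size is unstated.

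Reconcile the endpoint wording in SAP 4.2 and in Protocol sections 5 and 11.3.1 with the single-biopsy schedule. Record the change in SAP section 9, which now reads as not applicable. If the protocol is reworded to match, little remains to be recorded there.

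The cost is wording. The SAP edits are immediate. Rewording the protocol endpoint needs an amendment and the approvals in Protocol Appendix 3, so it could wait for the next one, with the SAP definition and the section 9 entry in place meanwhile. The one loss is that no within-patient change can be claimed, which the schedule never allowed. No additional procedure is proposed.
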